#### **8.0 Removal of Subjects from Study Treatment and Study**

---

Patients can be taken off the study treatment and/or study at any time at their own request, or they may be withdrawn at the discretion of the investigator for safety, behavioral or administrative reasons. The reason(s) for discontinuation will be documented and may include:

1. Patient completed study treatment;
2. Patient voluntarily withdraws from treatment (follow-up permitted);
3. Patient withdraws consent (termination of treatment and follow-up);
4. Patient/LAR is unable to comply with protocol requirements;
5. Patient demonstrates disease progression (unless continued treatment with study drug is deemed appropriate at the discretion of the investigator);
6. Patient experiences toxicity that makes continuation in the protocol unsafe;

7. Treating physician judges continuation on the study would not be in the patient's best interest;
8. Patient becomes pregnant (pregnancy to be reported along same timelines as a serious adverse event);
9. Development of second malignancy (except for basal cell carcinoma or squamous cell carcinoma of the skin) that requires treatment, which would interfere with this study;
10. Lost to follow-up.

If a research subject cannot be located to document survival after a period of 2 years, the subject may be considered "lost to follow-up." All attempts to contact the subject during the two years must be documented.

## **9.0 DATA AND SPECIMEN SUBMISSION GUIDELINES**

---

### **9.1 Labeling Samples**

Each sample to be labeled with patient specific study ID, initials, visit type, date of collection and time of collection.

### **9.2 Sample Collection Guidelines**

#### **MRD Testing**

For minimal residual disease testing, a first pull aspirate sample should be collected and sent overnight to the University of Washington or the facility designated by your local institutional guidelines for analysis. The aspirate should be collected in a 1mL to 5mL EDTA vial or according to local institutional guidelines.

#### **Gene Expression**

For gene expression testing, 2 mL will be collected from the bone marrow biopsy sample. In the event that there is a dry tap, the gene expression sample will be collected using peripheral blood if there are any circulating blasts present. If there are no circulating blasts, the gene expression sample will not be collected for testing. The sample needs to be processed immediately and carefully handled. Sites are responsible for providing their own tubes and vials for collection of all research related samples. In the event that a site does not have funding for supplies, the sample will not be collected and will not be considered a deviation. All samples will be shipped to and stored at UCI Clinical Trials Biospecimen Laboratory until analysis, which will be done at another laboratory. Please refer to the study sample lab manual for further processing, storage, and shipment instructions.

## **10.0 Measurement of Effect**

---

### **10.1 Antitumor Effect- Hematologic Tumors**

Response criteria for bone marrow are as per International Working Group Response Criteria in AML listed in Table 2.

## **10.2 Complete remission**

Complete remission is defined as no circulating blasts or extramedullary disease with a bone marrow biopsy with trilineage hematopoiesis with less than 5% blasts and ANC greater/equal than 1,000/uL and platelet count greater/equal than 100,000/uL.

Refractory disease is the failure to achieve CR at the end of induction.

Progressive disease is the increase of at least 25% in the absolute number of circulating or bone marrow leukemic blasts or appearance of extramedullary disease.

Relapsed disease is the reappearance of blasts in the bone marrow (greater than 5%) or in the blood after achieving CR or CRi.

MRD negative CR is the absence of detectable leukemic blasts using multiparameter flow cytometry at the University of Washington.

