## 2.2 Secondary Objectives/ Secondary Endpoints

2.2.1 Secondary Objectives	2.2.2 Secondary Endpoints

 
To evaluate any toxicities associated with the combination
 
	
 
Adverse events are to be captured and characterized by type, frequency, severity (as graded by NCI CTCAE v.5.0), timing, seriousness and relationship to study drugs
 

 
To evaluate the rate of response
 
	
 
The overall response rate (ORR) includes the rate of complete remission (CR) and complete remission with incomplete count recovery (CRi)
 

 
To evaluate the durability of response
 
	
 
Durability of response will be measured by relapse-free survival (RFS), defined as the amount of time a patient remains in remission after having achieved a CR or CRi
 

 
To evaluate survival and the length of survival
 
	
 
Survival follow up information will be collected to determine overall survival (OS)
 

 
To evaluate the time to return of normal hematopoiesis
 
	
 
Laboratory studies including complete blood counts (CBCs) will be collected to evaluate the recovery of bone marrow hematopoiesis
 

 
To evaluate the proportion of subjects who go on to receive allogeneic HSCT
 
	
 
HSCT information will be collected for patients who proceed to allogeneic HSCT
 

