### 5.4 Consolidation

Patients who achieve CR or CRi, can be continued on consolidation therapy for up to two cycles. In general, patients who have achieve CRi, consolidation should be initiated once the platelet count  $\geq$  50,000/uL and ANC  $\geq$  500/uL. The first consolidation cycle should start between 28 to 75 days after initiation of the last induction therapy. Each subsequent cycle of consolidation should be initiated between 28 to 55 days after the start of previous cycle of

consolidation. The exact day is at the treating physician's discretion. The number of consolidation cycles will depend on the time required for identification and availability of a suitable stem cell donor for patients going to stem cell transplantation.

The dose of CPX-351 will be at a dose of daunorubicin 29 mg/m^2–cytarabine 65 mg/m^2 on days 1 and 3. Glasdegib will be administered at 100mg daily for days 4-28. Consolidation cycles can last longer than 28 days. If cycles last more than 28 days, patient should continue to take glasdegib daily and as prescribed until day 1 of next cycle of CPX-351. Patient will be instructed to hold glasdegib on the day they receive CPX-351 infusion.

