### **7.2.3 Adequacy of bone marrow specimen**

An adequate bone marrow specimen is required to evaluate for remission (during induction days 28-60). An adequate bone marrow specimen is defined as having nucleated cells in the aspirate with spicules. The nucleated cell count is determined by the pathologist and the presence of spicules can be determined by the provider performing the bone marrow biopsy at the time of obtaining the aspirate. If the sample is inadequate, the bone marrow should be repeated within one week. In case of a dry tap without any aspirate, two cores are preferred; however, local institutional guidelines should be followed.

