## **10.4 Event-free survival**

Event-free survival is defined as the time from screening biopsy to the date of confirmed disease progression, relapse from CR/CRi, treatment failure, or death, whichever comes first. This was chosen as an endpoint for several reasons. It is known to incorporate several endpoints of interest including efficacy of the treatment as well as toxicity that both contribute to the outcome of the patient. Complete remission may not capture the full benefits of Glasdegib since the drug may prevent relapse through different mechanisms than enhanced cytotoxicity.

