**Appendix E. IWG Response Criteria****International Working Group Response Criteria in AML**

Classification	Definition
Complete remission (CR)	Bone marrow blasts < 5 percent; absence of blasts with Auer rods; absence of extramedullary disease; ANC > 1000/ $\mu$ L; platelet count > 100,000/ $\mu$ L; independence of red cell transfusions
Complete remission with incomplete hematologic recovery (CRi)	All CR criteria except for residual thrombocytopenia (platelet counts < 100,000/ $\mu$ L) and neutropenia (ANC < 1000/ $\mu$ L)
Complete remission with partial hematologic recovery (CRp)*	Bone marrow blasts < 5 percent; absence of blasts with Auer rods; absence of extramedullary disease; ANC > 500/ $\mu$ L; platelet count > 50,000/ $\mu$ L; independence of red cell transfusions
Morphologic leukemic-free state	Bone marrow blasts < 5 percent; absence of blasts with Auer rods; absence of extramedullary disease; no hematologic recovery required
Partial remission (PR)	Relevant in the setting of phase I and II clinical trials only; all hematologic criteria of CR; decrease of bone marrow blast percentage to 5 to 25 percent; and decrease of pretreatment bone marrow blast percentage by at least 50 percent
Cytogenetic remission	Reversion to a normal karyotype at the time of morphologic CR (or CRi) in cases with an abnormal karyotype at the time of diagnosis; based on the evaluation of 20 metaphase cells from bone marrow
Molecular remission	No standard definition; depends on molecular target
Resistant disease	Failure to achieve CR or CRi (general practice; Phase 2/3 trials), or failure to achieve CR, CRi or PR (Phase 1 trials); only includes subjects surviving $\geq$ 7 days following completion of initial treatment, with evidence of persistent leukemia by blood and/or bone marrow examination
Death in aplasia	Deaths occurring $\geq$ 7 days following completion of initial treatment while cytopenic; with an aplastic or hypoplastic bone marrow obtained within 7 days of death, without evidence of persistent leukemia
Death from indeterminate cause	Deaths occurring before completion of therapy, or < 7 days following its completion; or deaths occurring $\geq$ 7 days following completion of initial therapy with no blasts in the blood, but no bone marrow examination available
Relapse	Bone marrow blasts $\geq$ 5 percent; or reappearance of blasts in the blood; or development of extramedullary disease

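### Section 10.2 defines refractory disease by CR alone, against CR or CRi in the adopted response criteria, and the EFS event of treatment failure has no definition that would settle the conflict

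*Combined protocol and SAP*

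**What the plan says.** Section 10.2 gives the rule for failure: "Refractory disease is the failure to achieve CR at the end of induction". CRi is not mentioned there. A few lines later the same section defines relapse so that it can follow either response: "Relapsed disease is the reappearance of blasts in the bone marrow (greater than 5%) or in the blood after achieving CR or CRi".

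Sections 2.1 and 10.4 define EFS, whose six-month proportion (EFS6) is the primary endpoint. After disease progression, the listed events are "relapse from CR/CRi, treatment failure, or death, whichever comes first". No section says what treatment failure is, when it is assessed or how it is dated.

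Section 10.1 sets the governing criteria: "Response criteria for bone marrow are as per International Working Group Response Criteria in AML". It points to a Table 2; the IWG table that the document contains is Appendix E. There, resistant disease is "Failure to achieve CR or CRi (general practice; Phase 2/3 trials".

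Elsewhere CRi counts as a response. RFS in 2.2 is "defined as the amount of time a patient remains in remission after having achieved a CR or CRi", ORR in 2.2 is CR plus CRi, and 5.4 says "Patients who achieve CR or CRi, can be continued on consolidation therapy for up to two cycles".

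Two related terms add to the confusion. Section 5.3 calls a patient refractory when the blast count has not fallen at all, judged on the day-20 marrow. The footnote to the study schema names induction failure as a reason to stop treatment and does not define it.

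**The concern.** The gap would be harmless if treatment failure had its own definition. It has none, so whoever codes the event must find a rule, and the only one in the body of the protocol for the end of induction is the CR-only sentence in 10.2. Used that way, it gives one patient two contradictory statuses: in remission for ORR and RFS and eligible for consolidation, but already failed for EFS6.

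CRi-only patients are foreseeable. Section 1.5.3 reports prolonged recovery of cytopenias after CPX-351. Section 7.2.1 requires a marrow on day 60 if counts have still not recovered. Section 5.4 gives count thresholds for starting consolidation in CRi.

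Under 13.2.3, EFS6 alone decides whether the regimen merits further study, with up to five centers contributing patients (13.1). An event whose meaning has to be inferred can be coded differently from one patient to the next.

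Section 10.2 also leaves the end of induction open. Section 7.2.3 says "An adequate bone marrow specimen is required to evaluate for remission (during induction days 28-60", and 7.2.6 repeats the day-28-to-60 window for re-induction. No sentence says that this marrow is the one 10.2 means, or which course counts when re-induction is given.

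**Working it through.** **Step 1. The passages side by side.**

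| Place | How CRi without CR is treated |
|---|---|
| 10.2, refractory disease | Failure, if read literally |
| Appendix E, resistant disease, Phase 2/3 | Not a failure |
| 10.2, relapse | A remission from which relapse is possible |
| 2.1 and 10.4, EFS events | A remission from which relapse is possible |
| 2.2, ORR and RFS | A response |
| 5.4, consolidation | Continues protocol treatment |
| 2.1 and 10.4, treatment failure | Not stated |

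Only the first row makes CRi a failure. The EFS definition is itself informative. If CRi at the end of induction were already an event, the relapse term would be almost empty for CRi patients, because their first event would come before any relapse. The consistent reading is therefore that CRi is event-free and that the sentence in 10.2 is wrong as written.

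**Step 2. Check of the decision rule.** Section 13.2.3 uses the exact one-sided 90% lower bound, which must exceed 0.5. For x event-free patients out of n, the bound is the 0.10 quantile of a Beta(x, n − x + 1) distribution. The table in 13.3 for n = 28 reproduces with x = 28p:

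- p = 0.60, x = 16.8: 0.461 (table 46%)
- p = 0.65, x = 18.2: 0.511 (table 51%)
- p = 0.70, x = 19.6: 0.563 (table 56%)

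**Step 3. What one reclassified patient does.** The inputs are n from 28 to 30 (13.3) and the bound from step 2.

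| n | At the pass mark | One fewer event-free |
|---|---|---|
| 28 | 18: 0.504, pass | 17: 0.468, fail |
| 29 | 19: 0.519, pass | 18: 0.485, fail |
| 30 | 20: 0.534, pass | 19: 0.4999, fail |

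Each reclassified patient moves observed EFS6 by 1/28 = 3.6 points or 1/30 = 3.3 points. If the count is at least one above the pass mark, or already below it, recoding one CRi patient as a failure leaves the decision unchanged.

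**Step 4. What cannot be calculated.** The documents give combined CR/CRi rates for CPX-351 (for example 47% in the phase 3 trial, 1.5.3) but no rate for CRi without CR. The expected number of affected patients, and so the expected shift in EFS6, cannot be derived.

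**The case against.** The strongest reply is that nobody would code CRi as a failure. No sentence ties refractory disease in 10.2 to treatment failure in 10.4, and the adopted criteria, the relapse definition, ORR, RFS and consolidation all point the other way. On that reading the effect on EFS6 is zero. This stands as an account of what the protocol most likely intends. It does not remove the contradiction, and it does not supply the missing definition: the protocol states a rule that conflicts with its own criteria, next to an event that needs a rule.

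A second reply is that the reversals at the pass mark hold for any patient recoded for any reason. That is right. They show that the decision can turn on one patient, not that it is likely to do so here. CRi may also be transient, since 7.2.5 dates CR at later count recovery.

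Two stronger readings are tempting and are not supported:

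- A reader might infer that the plan counts CRi patients as EFS6 failures. The text as a whole says otherwise.
- A reader might infer that the 50% historical figure in 13.2.1 rests on a different failure rule. The document gives no failure rule for that figure, so no mismatch can be shown.

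A third reply concerns scope: treatment failure might also cover stopping for toxicity, starting other therapy without a response, or leaving before any remission marrow. The documents do not say. Correcting the CR/CRi conflict does not settle those cases.

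**Conclusion.** The point holds as an internal contradiction that bears on the primary endpoint. Section 10.2 is wrong as written, and treatment failure is neither defined nor dated. The likely intent can be recovered: CRi is not a failure.

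The size is bounded case by case and not overall. Each CRi patient coded as a failure who would otherwise be event-free at six months lowers observed EFS6 by 3.3 points (n = 30) to 3.6 points (n = 28). One such patient reverses the decision only at 18/28, 19/29 or 20/30. This rests on the exact bound in 13.2.3 and on a final evaluable sample of 28 to 30. It assumes nothing about how many CRi-only patients there will be. The correction should be made before events are coded; the point does not call the design into question.

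**What to change.** In 10.2, replace the sentence with: *Refractory disease is failure to achieve CR or CRi by the remission marrow of the last induction course, including re-induction if given (day 60, or the repeat marrow allowed by 7.2.3).* The reference to the repeat marrow is needed because 7.2.3 asks for an inadequate sample to be repeated within a week, which can fall after day 60.

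In 2.1 and 10.4, add: *Treatment failure means refractory disease as defined in 10.2, or removal as refractory on the day-20 marrow under 5.3, dated at the marrow that shows it. CRi, with either or both cytopenias, is not a treatment failure.* The words on cytopenias are needed because Appendix E joins thrombocytopenia and neutropenia with *and*. Read literally, a patient with only one of them would be neither CR nor CRi.

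While making this edit, the sponsor should decide whether stopping for toxicity, starting other therapy without a response, or leaving before a remission marrow is an event. The wording above does not decide these cases.

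The cost is one sentence in 10.2 and two in each of 2.1 and 10.4, with no added visits, tests or patients.

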## **10.3 Progressive disease**

Progressive disease is the evidence for an increase in bone marrow blast percentage and/or increase of absolute blast counts in blood by 50% or new extramedullary disease.

## **10.4 Event-free survival**

Event-free survival is defined as the time from screening biopsy to the date of confirmed disease progression, relapse from CR/CRi, treatment failure, or death, whichever comes first. This was chosen as an endpoint for several reasons. It is known to incorporate several endpoints of interest including efficacy of the treatment as well as toxicity that both contribute to the outcome of the patient. Complete remission may not capture the full benefits of Glasdegib since the drug may prevent relapse through different mechanisms than enhanced cytotoxicity.

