**SCHEDULE OF EVENTS**

Protocol Activity	Screening	Induction/ Re-induction E (Days 1-75)							Consolidation J (Days 1-55)				Maintenance K (Days 1-28)	EOT	Follow-up
	≤ 28 days prior to D1	D1	D3	D5	D6	Weekly (+/- 2 days)	Induction response D20 (+1 day)	Remission evaluation D28 to D60	D1	D3	D4	Weekly (+/- 2 days)	D1 (+/- 7 days)	Within 7 days of last dose	Every 3 month (+/- 14 days)
Informed Consent A	X														
Clinical Evaluation and Procedures															
Eligibility Review	X														
Disease Classification	X														
Medical History	X														
Concomitant Medication Review	X	For the entire duration of study participation													
AE/ SAE Review		From when participant start study therapy on induction day 1 up until 28 days after the last dose of study therapy/ and until resolution of any treatment-related AE/ SAE													
Physical Exam	X	X				X			X			X	X	X	X
ECOG Performance	X	X				X			X			X	X	X	X
12-lead ECG	X				X G	X G,H					X G			X	
ECHO	X														
BMA/BMBX	X C						X	X				X N		X L	
MRD (send to UW)							X	X						X L	
Cytogenetics /Molecular profiling	X C						X	X						X L	

Research sample for gene expression correlatives	X C, D						X D	X D						X D,L	
HSCT information/ Survival Status															X M
Laboratory Assessments															
Hematology	X	X				X	X	X	X			X	X	X	X
Chemistry	X	X				X			X			X	X	X	
Urinalysis	X														
Coagulation	X														
Pregnancy Test B	X								X				X		
Study treatment															
CPX-351 Infusion		X	X	X F					X	X					
Glasdegib					X I						X I		X		

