**Footnotes:**

- A Must be obtained before undergoing any protocol-specific study procedures, unless as part of standard of care
- B Serum beta-HCG should be done for any female of child-bearing potential
- C Bone marrow collections do not need to be repeated if a diagnostic bone marrow procedure was done prior to informed consent and is done within 28 days of starting day 1 of induction
- D Collect bone marrow aspirate for research sample for gene expression correlatives; if patient has any circulating blasts, then peripheral blood can be collected instead of aspirate; if bone marrow is a “dry tap,” then this sample does not need to be collected
- E Re-induction is based on response evaluation bone marrow done on day 20 of induction. If there is greater than 5% blast count, re-induction is recommended. The final decision for re-induction is based on investigator’s discretion. For patients who will be treated with re-induction, an ECHO and pregnancy test (for female patients of child-bearing potentials) will be done before starting re-induction
- F Omit CPX-351 on day 5 for participants receiving re-induction

G ECG is done pre-dose and can be done up to 24 hours before planned glasdegib dosing

H During induction, repeat an ECG a week after starting glasdegib (around day 13-15). If clinically significant abnormal ECG or clinically significant changes in QTc, then refer to section 6.4 for further guidance. If normal or non-clinically significant abnormalities and/or changes in QTc, additional ECG monitoring is not required and is done per the treating investigator's discretion

I Glasdegib should continue until day 1 of the next cycle of CPX-351

J Up to two cycles of consolidation is allowed. These are 28 day cycles, unless delays are necessary. In the case of a delay, glasdegib will continue daily until the start of CPX-351 infusion in the next cycle. If the patient will proceed to allogenic SCT, then consolidation can be skipped or shorten. Glasdegib will be stopped at least 7 days before transplant.

K These are 28 days cycle. Patients who are not receiving HSCT will be allowed to proceed to glasdegib maintenance for up to 1 year of study start

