### **7.1 Screening/Baseline Procedures**

Assessments performed exclusively to determine eligibility for this study will be done only after obtaining informed consent. Assessments performed for clinical indications (not exclusively to determine study eligibility) may be used for baseline values even if the studies were done before informed consent was obtained.

All screening procedures must be performed within 28 days prior to registration unless otherwise stated. The screening procedures include:

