## **10.5 Final Response Assessment**

Overall survival is measured as the time from the date of diagnostic biopsy which confirmed disease to the date of death from any cause. Patients not known to have died at last follow-up are censored on the date they were last known to be alive. Patients will be followed for a minimum of one year from the completion of the treatment.

Patients who go on to allogeneic transplant will be censored for survival on the dates that they start conditioning regimen to avoid transplant as a confounding factor in analysis of overall survival.

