### 13.2.2 Primary Endpoint

The primary endpoint for efficacy is EFS6. The event-free interval begins with the date of diagnostic biopsy, and ends as described in Section 2.1.

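### EFS6 and OS are timed from a biopsy taken before Day 1, so part of the six months is event-free by construction; the go rule's false-positive rate rises if the historical 50% runs from a later start

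*Combined protocol and SAP*

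**What the plan says.** Section 10.4 gives the definition: "Event-free survival is defined as the time from screening biopsy to the date of confirmed disease progression". Section 2.1 says the same. Section 13.2.2, which governs the primary analysis, names a different marrow: "The event-free interval begins with the date of diagnostic biopsy". For OS, section 10.5 says: "Overall survival is measured as the time from the date of diagnostic biopsy which confirmed disease".

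The Schedule of Events sets the screening window at "≤ 28 days prior to D1". Its footnote C waives a repeat marrow when "a diagnostic bone marrow procedure was done prior to informed consent and is done within 28 days of starting day 1 of induction". Section 7.1 uses another anchor: "All screening procedures must be performed within 28 days prior to registration unless otherwise stated". Section 7.1.4 requires participating sites to send the marrow report at least 3 business days before the planned start of treatment.

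Sections 13.2.1 and 13.2.3 compare EFS6 in evaluable participants with a historical 50%. The regimen passes if the exact one-sided 90% lower limit exceeds 0.5. Neither section gives the source of the 50% or the date from which it was counted, and the plan does not define evaluable for efficacy.

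**The concern.** A time-to-event clock should start no earlier than the point at which a patient can enter the analysis. Here it starts at a marrow that can precede consent. Anyone who dies between that marrow and study entry leaves no record, so everyone who is analysed has survived the interval. If evaluable means dosed, this applies to the whole interval from biopsy to Day 1.

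Two things follow whatever the benchmark is. A site that takes longer to start treatment reports a higher EFS6 with no change in drug effect. And patients with different gaps are read at different times after first dose. The induction assessments, by contrast, are all timed from Day 1.

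A third consequence depends on the benchmark. This is a single-arm trial whose go decision rests on a comparison with a fixed 50%, and no concurrent control shares the bias. If the 50% was counted from a later start, an ineffective addition is more likely to pass.

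**Working it through.** **Inputs.** Landmark: six months, taken as 182.6 days. Null 50%, with the exact one-sided 90% lower limit to exceed 0.5 (13.2.3). Sample size: 28 or 30 evaluable (13.3). Gap L from biopsy to Day 1: up to 28 days (Schedule of Events, footnote C). The documents give no distribution of gaps, so L is an assumption and is shown over a range.

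**Step 1, the plan's own bounds.** The Clopper-Pearson lower limit for x out of n is the 10th percentile of Beta(x, n − x + 1). With n = 28 and x = 28 × 0.60, 28 × 0.65 and 28 × 0.70 it gives 0.461, 0.511 and 0.563. These match the 46%, 51% and 56% tabulated in 13.3.

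**Step 2, the pass mark.**
- n = 28: 17 event-free gives 0.468 (fail) and 18 gives 0.504 (pass).
- n = 30: 19 gives 0.4999 (fail) and 20 gives 0.534 (pass).

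At a true 50%, P(X ≥ 18 | n = 28) = 9.2% and P(X ≥ 20 | n = 30) = 4.9%.

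**Step 3, the gap under constant hazard.** Assume that 50% is the true rate at 182.6 days from first dose. With the clock started L days earlier, the recorded EFS6 is S(182.6 − L) = 0.5^((182.6 − L)/182.6). For L = 14 this is 0.5^(168.6/182.6) = 0.527. For L = 28 the read falls 182.6 − 28 = 154.6 days after first dose, and the value is 0.5^(154.6/182.6) = 0.556. Putting these values into the binomial tails gives:

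| Gap in every patient | Recorded EFS6 when truth is 50% | False positive, n = 28 (≥18) | False positive, n = 30 (≥20) |
|---|---|---|---|
| 0 days | 50.0% | 9.2% | 4.9% |
| 7 days | 51.3% | 11.9% | 6.6% |
| 14 days | 52.7% | 15.0% | 8.8% |
| 21 days | 54.1% | 18.8% | 11.6% |
| 28 days | 55.6% | 23.3% | 15.0% |

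Taking six months as 183 days changes these by at most 0.1 percentage point. With 28 subjects, a 3-day gap already exceeds the nominal 10% (recorded EFS6 50.6%, rate 10.3%). With 30 subjects, the rate is 9.9% at 17 days and 10.3% at 18 days, so the nominal level is passed at about two and a half weeks.

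**Step 4, early failures.** Suppose a fraction e fails early and the rest have constant hazard λ = ln((1 − e)/0.5)/182.6, so that EFS at 182.6 days is still 50%. Then S(154.6) = (1 − e) × exp(−154.6λ).
- e = 0.40: 0.6 × exp(−154.6 × ln(1.2)/182.6) = 51.4%. At a 28-day gap the false-positive rates are 12.0% (n = 28) and 6.7% (n = 30).
- e = 0.45: 50.7%, with rates of 10.6% and 5.8%.

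An intermediate case sets the hazard near month six at half the average: 0.5 × exp(0.5 × ln 2 × 28/182.6) = 52.7%, with rates of 15.0% and 8.8%.

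**Step 5, benchmark on the same clock.** If the 50% was also counted from biopsy with a similar gap, the rates stay at 9.2% and 4.9%.

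**The case against.** The strongest objection is that the rise in false positives is conditional. A reader might infer that the plan's error rate is inflated as a matter of fact. The documents do not support that, because they never say when the historical clock began. This objection stands, and the conclusion is worded accordingly.

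The size is also open to challenge. The figure of 23.3% needs the maximum gap in every patient and a constant hazard. Treatment failure counts as an event, section 10.2 calls refractory disease at the end of induction, and section 1.5.3 reports a CR/CRi rate of 47% on CPX-351. Many events may therefore fall early, leaving a low hazard near month six, so the smaller figures in step 4 are realistic. At the accrual goal of 30, gaps of one or two weeks stay below 10% even under constant hazard.

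Three other stronger readings are tempting.
- **Gaps longer than 28 days.** Section 7.1 counts from registration, which might suggest this. But that sentence yields to more specific statements, and the Schedule of Events and footnote C tie the marrow to Day 1. The diagnostic biopsy in 13.2.2 has no date limit of its own if it is not the screening marrow, but nothing here relies on that.
- **The whole gap being event-free for every patient.** Section 4.1 enters consented patients in OnCore on the day of consent, and a study-specific marrow can follow consent. Because evaluable is undefined, a death between consent and Day 1 might be counted. Only the time from a pre-consent biopsy to study entry is event-free on every reading.
- **A false-positive rate for OS.** OS is described by Kaplan-Meier methods with no fixed null, so none exists.

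None of this removes the core point: under the present definition, delay before treatment raises the primary endpoint.

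**Conclusion.** The concern holds in conditional form. EFS6 and OS start at a marrow that may precede consent and may be up to 28 days before Day 1. The time from a pre-consent biopsy to study entry is event-free by construction, and so is the whole gap to Day 1 if evaluable means dosed. That bias does not depend on the benchmark.

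The effect on the go rule rests on three assumptions: the 50% is counted from randomisation, registration or first dose; the gap has the assumed length in all patients; and the hazard has the assumed shape. With constant hazard and gaps of one to two weeks, the false-positive rate is 11.9% to 15.0% at n = 28 (9.2% with no gap) and 6.6% to 8.8% at n = 30 (4.9% with no gap). The worst case is 23.3% and 15.0%. If most failures occur early, a 28-day gap gives about 11% to 12% and 6% to 7%. If the benchmark is biopsy-based with a similar gap, there is no inflation. OS carries the same lead-time bias, but no error rate attaches to it.

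**What to change.** - In 2.1, 10.4, 10.5 and 13.2.2, start EFS and OS on Day 1 of induction, or at registration, with one wording throughout. This also removes the conflict between the screening and the diagnostic biopsy. Keep biopsy-based time as a sensitivity analysis.
- In 13.2, state the source and time origin of the 50% and express it on the same clock. Say whether evaluable requires a dose, so that the analysed set matches the chosen start.
- In 7.1, count the 28-day marrow window back from Day 1, as the Schedule of Events does.

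The cost is a wording amendment; the date of the first CPX-351 infusion is already recorded. Reported EFS6 and OS become slightly less favourable. If the 50% proves to be biopsy-based, it must be re-expressed from the new start, or the mismatch reverses. Under constant hazard with a 14-day gap, a true 65% would then read as 0.65^((182.6 + 14)/182.6) = 62.9%, and exact power at n = 28 would fall from 61.6% to 52.4%. The 61.6% is the recomputed power of the rule in 13.2.3 and differs from the figure of at least 90% in 13.3, which is a separate matter.
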